## **10. DATA COLLECTION AND QUALITY ASSURANCE**

### **10.1 Data Collection Forms**

Consented patients' data (including screening questions, demographics, and the survey on mouth rinse acceptability) will be collected using the CDART dental toolkit program, which stores data on a secure UNC maintained server and meets federal guidelines for clinical study data acquisition. The CDART electronic forms and database will serve as our CRFs and source data. IRB approved study personnel will ask participants the questions and will enter responses into this encrypted, password protected database. Data will be collected in this program using participant's study ID and no other personal health identifiers (PHI). A separate linkage file, securely stored on UNC servers, will be utilized to associate the random alphanumeric study ID with patient identifier, so samples and data will not be associated with patient identifiers. Data will only be transmitted among the research team using the school of dentistry secure research servers. Demographic data will be transmitted among the research team through access to the secure CDART research database system, stored on secure UNC servers, which study personnel will access only through encrypted computers via secure user accounts.

### **10.2 Data Management**

An Excel key will be created with study ID (random alphanumeric code) to identify patients, saved in a secure folder on a UNC SOD server. This linkage file will be stored separately from data and destroyed at the close of the study. All data collected from participants and results from sample analysis will be coded with unique numerical identifiers and stored in the UNC CDART clinical research database and on a secure UNC-CH server. Only trained, IRB-approved study personnel will enter and access data in the secure CDART research database.

Consented patients' data (including screening questions, demographics, and the survey on mouth rinse acceptability) will be collected using the CDART dental toolkit program, which stores data on a secure UNC maintained server and meets federal guidelines for clinical study data acquisition. Only HIPAA and human subjects trained, IRB-approved study personnel will collect, enter and manage patient data; study coordinators will serve in this capacity.

Data will be collected in the CDART research database using participant's study ID and no other PHI identifiers, on approved, carefully designed digital forms within CDART. CDART forms will include questions with drop downs, radio button multiple choice and text field entry, depending on the question type. There will be separate digital forms for inclusion/exclusion screening questions (before sample collection begins), demographic

questions, and questions regarding mouthrinse experience (taste, color, sensation) and willingness to use a mouthrinse in various clinical settings (e.g. dentist or doctor appointments). A separate linkage file, securely stored on UNC servers, will be utilized to associate the random alphanumeric study ID with patient identifier, so samples and CDART data will not be associated with patient identifiers.

Data will only be transmitted among the research team using the SOD secure research server. Demographic data will be transmitted among the research team through access to the secure CDART research database system, stored on secure UNC servers, which study personnel will access only through encrypted computers via secure user account.

Linkage files containing identifiers will be deleted and permanently removed from all servers and study computers at the conclusion of the study with acceptance of associated manuscripts. Saliva specimens will be labeled with a study ID (random alphanumeric code) that is not identifiable without the linkage file, and therefore will not be identifiable after linkage file destruction.

The quality control committee (described below) will be in charge of monitoring these forms and the CDART database.

### **10.3 Quality Assurance**

#### **10.3.1 Training**

All study personnel have been trained in health privacy (HIPAA) and human subjects research through the CITI program and are certified to work with patient data on clinical trials. Study coordinators and healthcare providers are trained in and approved for the use of the CDART electronic research database and EPIC medical record system. Technical research personnel performing viral PCR and infectivity assays are approved to operate in their BL3 laboratory facilities and have specialized, lab-based training in these molecular techniques. They have also undergone training in the use of universal precautions and management of human biological samples along with bloodborne pathogen training. Finally, the GoHealth Clinical Research core has highly experienced research coordinators who will monitor all study staff to ensure protocol compliance and quality assurance.

#### **10.3.2 Quality Control Committee**

The investigators and study coordinators will meet weekly as an internal quality control committee to review consent documents, CDART data forms, and unanticipated problems with recruitment or adverse events. There is only one site for this study. The use of on-label, widely used mouthrinses (like Listerine or Crest) and collection of saliva carry minimal risk for participants, apart from the very rare, undiagnosed allergy, which

would be managed through proper referral to the neighboring UNC hospital. Therefore, there is no study quality control committee.

### **10.3.3 Metrics**

Every salivary sample will be collected in a conical tube with millimeter markings to monitor salivary volume. If insufficient saliva is collected, the study personnel collecting the samples from participants will note insufficient volume in the CDART database for each applicable time point and will indicate in CDART if the subject must be withdrawn and replaced. If a patient is unable to generate sufficient saliva for the 0 min, 15 minutes or 30 minutes post-rinse time points, the subject will be removed from the study and this will be noted in CDART along with their insufficient samples. If a subject is unable to generate sufficient saliva for time points 45 or 60 minutes post-rinse, the patient will remain in the study but their insufficient samples will be noted in CDART.

For qRT-PCR, viral infectivity, and sandwich ELISA or rapid antigen assays, all salivary samples will be run in triplicate with standard experimental controls (negative and positive) and protocol quality checks performed by research technical personnel in the COVID core, [name], and [name] laboratories.

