### **Randomization**

Our statistician [name] will create a block randomization schedule and perform these computations. All patients will be consented and then fill out our screening questions for inclusion and exclusion to confirm eligibility prior to being assigned to the randomization schedule.

The researcher in charge of collecting the salivary samples will be blinded to the mouthwash solution, as they will be given a pre-aliquoted mouthrinse in an unlabeled storage tube to provide to the patient for the rinse.

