#### **6.2.5 Completion/Final Evaluation**

This study requires only one 70-90 minute, single visit appointment. Subjects will be asked to rinse with an unlabeled/blinded antiviral mouth rinse for 60 seconds and provide 5 mL of saliva prior to the rinse and 2 mL of saliva immediately post-rinse, 15 minutes post-rinse, 30 minutes post-rinse, 45 minutes post-rinse, and 60 minutes post-rinse. Subjects will also be asked to complete a short survey about the rinsing experience.

Subjects may withdraw from the trial at any time at their own request, or they may be withdrawn at any time at the discretion of the Investigator or Sponsor for safety, behavioral or administrative reasons.

The Investigator may discontinue a subject if, in the opinion of the Investigator, the subject is no longer a suitable candidate for the study. Possible reasons for the discontinuation of a subject are including but not limited to: adverse event, protocol deviation, missed appointment, subject no longer meets the eligibility criteria.

Patients may be removed from the study due to an allergic reaction to a mouth rinse or due to failure or inability to comply with study procedures.

If a patient suffers from xerostomia/dry mouth, such that s/he cannot produce the baseline salivary sample volume or the immediate, 15 minute and 30 minute post-rinse saliva volumes, s/he will be removed from the study with a parking voucher, but without a gift card and will be replaced. If a patient suffers from dry mouth, such that s/he cannot produce salivary sample volumes needed for later time points (45 minutes or 60 minutes post-rinse) but s/he produced sufficient baseline, immediate, 15 minute and 30 minute post-rinse samples, s/he will still be compensated with a gift card and parking vouchers, and will remain in the study. Missing or deficient salivary samples will be noted in CDART.

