## **8. INTERVENTION DISCONTINUATION**

Subjects may withdraw from the trial at any time at their own request, or they may be withdrawn at any time at the discretion of the Investigator or Sponsor for safety, behavioral or administrative reasons.

The Investigator may discontinue a subject if, in the opinion of the Investigator, the subject is no longer a suitable candidate for the study. Possible reasons for the discontinuation of a subject are including but not limited to: adverse event, protocol deviation, missed appointment, subject no longer meets the eligibility criteria.

Patients may be removed from the study due to an allergic reaction to a mouth rinse or due to failure or inability to comply with study procedures.

If a patient suffers from xerostomia/dry mouth, such that s/he cannot produce the baseline salivary sample volume or the immediate, 15 minute and 30 minute post-rinse saliva volumes, s/he will be removed from the study with a parking voucher, but without a gift card and will be replaced. If a patient suffers from dry mouth, such that s/he cannot produce salivary sample volumes needed for later time points (45 minutes or 60 minutes post-rinse) but s/he produced sufficient baseline, immediate, 15 minute and 30 minute post-rinse samples, s/he will still be compensated with a gift card and parking vouchers, and will remain in the study. Missing or deficient salivary samples will be noted in CDART.

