### 9.5.1 Primary Outcomes

The primary objectives of this study are to determine the efficacy of antiseptic mouthwashes on reducing SARS-CoV-2 viral RNA and protein antigen levels in COVID+ patient saliva. *We hypothesize that COVID-19+ patients will have a >95% reduction in SARS-CoV-2 viral RNA and protein antigen levels following a 60 second oral rinse with an antiseptic mouthrinse and that this reduction will persist for at least 30 minutes.* These primary objectives will assess SARS-CoV-2 viral load based on viral RNA measured by quantitative real time PCR and viral protein antigen levels measured by rapid antigen or sandwich ELISA assays. These objectives provides urgently needed data to guide healthcare workers on the proper use of specific commercially available

mouthwashes capable of reducing SARS-CoV-2 in saliva and potentially limiting COVID-19+ transmission.

Outcome assessments will be conducted weeks to months after the study visit, when qRT-PCR and sandwich ELISA or rapid antigen assays are conducted in the COVID core and the [name] lab.

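### Patients who have rinsed are removed and replaced for insufficient saliva at 0, 15 or 30 minutes, and no analysis set or missing-data method keeps them in their assigned arm

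*Combined protocol and SAP*

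**What the plan says.** **Order of events.** Under Randomization in section 6.2.2, patients answer the screening questions to "confirm eligibility prior to being assigned to the randomization schedule". Section 5.1 then has the baseline sample, the rinse and the post-rinse samples, in that order. A post-rinse shortfall therefore comes after both allocation and exposure.

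**Removal rule.** Section 10.3.3 has the collecting staff record short samples; they "will indicate in CDART if the subject must be withdrawn and replaced". Its next sentence rules, for anyone "unable to generate sufficient saliva for the 0 min, 15 minutes or 30 minutes post-rinse time points, the subject will be removed from the study". For a shortfall at 45 or 60 minutes, "the patient will remain in the study but their insufficient samples will be noted in CDART".

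**The same rule elsewhere.** Sections 6.2.5 and 8 share one paragraph. It removes a patient when "s/he cannot produce the baseline salivary sample volume or the immediate, 15 minute and 30 minute post-rinse saliva volumes", and then "s/he will be removed from the study with a parking voucher, but without a gift card and will be replaced". The next sentence keeps a patient who is short only at the later time points, on condition that "s/he produced sufficient baseline, immediate, 15 minute and 30 minute post-rinse samples, s/he will still be compensated with a gift card".

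**Outcome and analysis.** The primary hypothesis in section 9.5.1 is a reduction of more than 95% "following a 60 second oral rinse with an antiseptic mouthrinse and that this reduction will persist for at least 30 minutes". The interim rule in section 9.4 drops arms on infectivity at 15 and 30 minutes, with 20 patients per arm. Section 9.3 restates eligibility. Sections 9.1 and 9.6 name t, Mann-Whitney, logistic regression and ANCOVA methods, but no analysis set, no rule for the samples of removed patients and no method for missing values.

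**The concern.** Whether a patient counts depends on something measured after the assigned rinse, inside the window that the primary hypothesis addresses. Replacement restores the number per arm but not the randomised comparison: the arms compared are those patients who went on to give enough saliva for 30 minutes.

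This biases the comparison between rinses only if two things hold together: shortfall differs by rinse, and it is related to the change in viral load given baseline. The documents do not show that six different solutions leave saliva output equal. The adverse-effect tables in sections 2.2 and 7 list dry mouth and salivary gland inflammation among reports for one rinse. Those are product-label reports, not evidence about a single rinse, but they mean that an effect on saliva cannot simply be assumed away.

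The interim is the more exposed analysis, because removal acts on the same early time points that decide whether an arm continues, and the arms are small.

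**Working it through.** **Plan's figures.** The documents give no shortfall rate and no difference in response between patients who can and cannot give saliva. There is no figure of the plan's to reproduce for the bias, and everything under steps 1 to 4 is illustration.

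**Assumed inputs.** Chance of a short sample at each of the three time points, p = 0.01 to 0.05. Gap in log10 reduction between retained and removed patients, g = 0.5 to 1.0.

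1. *Share of an arm removed, f, when any one short sample removes the patient.*
   - Failures fully correlated within a patient: f = p = 1% to 5%.
   - Failures independent: f = 1 − (1 − p)³ = 1 − 0.99³ = 3.0% to 1 − 0.95³ = 14.3%. This is the upper bound.
   - In between, a simulation at p = 0.05 with an assumed correlation of 0.5 or 0.8 between a patient's saliva volumes gave 11.8% and 9.2%.
   - If all three samples had to be short, independent failures would give p³, at most 0.0125%, and full correlation again 1% to 5%.

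2. *Patients who must rinse to keep 80:* 80/(1 − f). Correlated: 80/0.99 = 80.8, so 81, to 80/0.95 = 84.2, so 85. Independent: 83 to 94.

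3. *Removed per 20 kept at the interim:* 20/(1 − f) − 20. Correlated: 0.2 to 1.1. Independent: 0.6 to 3.3.

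4. *Shift between two arms,* one with p = 5% and one with p = 1%: (f₁ − f₂) × g.
   - Correlated: (0.05 − 0.01) × 0.5 = 0.02 to (0.05 − 0.01) × 1.0 = 0.04 log10. As a ratio of viral loads this is 10^0.02 = 1.05 to 10^0.04 = 1.10.
   - Independent: (0.1426 − 0.0297) × 0.5 = 0.06 to (0.1426 − 0.0297) × 1.0 = 0.11 log10.
   - Equal shortfall and equal gap in both arms: zero.
   - For scale, a 95% reduction is −log10(0.05) = 1.30 log10.

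5. *Does power require replacement?* The plan states n = 78 for a paired t-test at d = 0.7, 80% power and alpha 0.016. A two-sided noncentral-t calculation gives 25, so 78 is not reproduced; that is a separate matter and nothing here rests on it. For the between-rinse comparison at the plan's d = 0.7, use a two-sample t-test with noncentrality d × √(n/2). If 80 are randomised per arm and 5%, 10% or 20% lack complete samples to 30 minutes, 76, 72 or 64 remain:

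| Complete per arm | Power, alpha 0.016 | Power, alpha 0.005 (0.05/10) |
|---|---|---|
| 76 | 96.9% | 92.7% |
| 72 | 96.0% | 90.9% |
| 64 | 93.4% | 86.2% |

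On the plan's own effect size, replacement is not needed to hold 80% power.

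**The case against.** The strongest reply is that little is at stake. Xerostomia is an exclusion (section 4.2). The baseline demand, 5 mL in 10 minutes or 0.5 mL/min, exceeds the post-rinse one, 2 mL in 5 minutes or 0.4 mL/min. The collector is blinded (sections 6.2.2, 6.2.3 and 9.2), and shortfalls are logged in CDART and reviewed weekly (sections 10.3.3 and 10.3.5). This stands as a reason to expect few removals and little discretion over them. It does not exclude a rinse effect on saliva, and nothing in the plan says that the logged shortfalls are reported by arm or handled in the analysis.

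A reader might infer several stronger things that the documents do not support:

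- *That the sections contradict each other on the trigger.* Section 10.3.3 joins the time points with 'or', and sections 6.2.5 and 8 with 'and'. But the next sentence of 6.2.5 and 8 keeps only patients whose early samples were all sufficient, which favours 'or'. The wording needs tidying. The plainer difference is that the removal sentence of 10.3.3 leaves out the pre-rinse baseline.
- *That the cut-off is 2 mL.* No section defines a sufficient volume. The figure is inferred from the collection target, and the flow comparison above rests on the same inference. A lower cut-off would mean fewer removals.
- *That samples already given by removed patients are discarded.* No section says so. They are removed, replaced and give no later samples, and no analysis set brings them back.
- *That an interim decision would change.* Section 9.4 gives no numerical criterion for an ineffective rinse, so this cannot be shown. Three removals per 20 arises only under independent failures.

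**Conclusion.** The point holds in this form: a stated rule conditions inclusion on a post-rinse result, and the plan has no analysis set or missing-data method to offset it. The size and direction of any bias cannot be obtained from the documents. The bias is probably small. With fully correlated failures, an assumed 5% against 1% shortfall and an assumed gap of 0.5 to 1.0 log10, it is 0.02 to 0.04 log10, against a hypothesised reduction of 1.30. Independent failures raise this to 0.06 to 0.11 log10 as an upper bound.

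The claim that the primary comparison *is* biased would go too far, because that needs a rinse effect on saliva for which the documents give no evidence. The change should still be made: the plan already contains the better rule for 45 and 60 minutes, and power at d = 0.7 does not depend on replacement.

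**What to change.** The changes concern saliva-volume failures only. Withdrawal for safety, allergy, non-compliance or at the patient's request stays as it is.

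1. In sections 6.2.5, 8 and 10.3.3, treat a post-rinse shortfall at 0, 15 or 30 minutes as one at 45 or 60 minutes is treated now: keep the patient, flag the sample in CDART, do not replace. Limit volume-based replacement to failure of the baseline sample, which precedes the rinse.
2. In section 9.3, define the primary analysis set as all randomised patients who rinsed, in the assigned arm.
3. In section 9.6, analyse all available log10 values adjusted for baseline, for example with a repeated-measures extension of the planned ANCOVA. Assay short samples for RNA and antigen wherever the 500 µL aliquot exists (0.5/2.0 = 25% of the collection target).
4. Report short and missing samples by arm at the interim and final analyses, including missing infectivity values alongside the arm-dropping decision.
5. Reconcile sections 6.2.5 and 8 with 10.3.3 on the joining word, the baseline trigger and the volume that counts as sufficient.

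**Cost.** Some series will be incomplete, with slightly fewer than 80 complete profiles per arm. A short sample may not supply every assay, and a patient with no post-rinse sample still contributes no outcome. The gift-card rule is tied to removal and must be aligned. The modification needs IRB review (section 11.1). The by-arm table uses data that CDART already records.

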### **10.3.4 Protocol Deviations**

Protocol deviations will be recorded within the source documentation for each participant within the CDART study database by study personnel during the study visits. The investigators and study coordinators will meet weekly to review unanticipated problems, adverse events and protocol deviations recorded in the CDART study database. All such events will be appropriately reported to the IRB board of UNC.

### **10.3.5 Monitoring**

The quality control committee will meet weekly to review adverse events, protocol deviations, data quality in CDART, and collection of consent forms. The GoHealth Clinical Research core has highly experienced research coordinators who will monitor all study staff to ensure protocol compliance. A representative from the GoHealth core will participate in the weekly quality control committee meetings to review CDART records and consent forms.

## **11. PARTICIPANT RIGHTS AND CONFIDENTIALITY**

### **11.1 Institutional Review Board (IRB) Review**

This protocol and the informed consent document and any subsequent modifications will be reviewed and approved by the IRB or ethics committee responsible for oversight of the study. Consent forms are separate from this protocol document and were submitted as part of the IRB application.

### **11.2 Informed Consent Forms**

Outpatients, who have tested positive for COVID-19 and consented to be contacted for study enrollment in the UNC Respiratory Distress Clinic (RDC), will be contacted to participate in this study by research personnel. The subjects being approached by phone or email have signed a prior facility consent at the Respiratory Distress Clinic confirming their willingness to share their name and contact information to be contacted for study participation in COVID related research. We will not receive information on subjects that decline this internal consent. Patients will be contacted first by phone and, if not available, then by email. The study's purpose and requirements will be explained and the patient will have the opportunity to ask questions and will have time to consider participation. Interested patients will make an appointment to visit the Go Health Clinical Research Unit at Adams School of Dentistry for this study. Study participation includes only one visit. The consent forms will be reviewed and signed by interested patients in person in the Go Health Clinical Research Unit at Adams School of Dentistry.

A signed consent form will be obtained from each participant. For participants who cannot consent for themselves, such as those with a legal guardian (e.g., person with power of attorney), this individual must sign the consent form, though minors and patients who are intellectually delayed and unable to consent for themselves will be excluded. The consent form will describe the purpose of the study, the procedures to be followed, and the risks and benefits of participation. A copy will be given to each participant or legal guardian and this fact will be documented in the participant's record. For Spanish speaking patients and/or parents, Spanish forms will be provided and communication will occur through a Spanish translator. All patients are adults and over normal cognitive capacity, and therefore will be able to consent for themselves.

At the visit, a consented patient will answer screening questions regarding inclusion and exclusion criteria. Answers will be entered into the CDART research database managed by UNC. Prior to finalizing these screening questions, women participants of childbearing potential will be asked to provide a urine sample in the restroom, to undergo a rapid pregnancy test by study personnel. Any pregnant or lactating patients will be excluded.

Our study statistician, [name], will create a block randomization schedule and perform these computations. All patients will be consented and then fill out our screening questions for inclusion and exclusion to confirm eligibility prior to being assigned to the randomization schedule.

